4 STATISTICAL/ANALYTICAL ISSUES

4.1 Adjustments for covariates

There will be no adjustment for covariates.

4.2 Handling of dropouts or missing data

Missing data will be handled as described in the sections below for efficacy, safety and PK results. No other imputations will be performed.

4.2.1 Efficacy data

4.2.1.1 Psoriasis Area and Severity Index

Missing data for the individual items of the PASI score will be imputed as described in [Section 8.1.1](#) in order to calculate the PASI score at each visit.

The primary efficacy variable is change from Baseline in PASI at Week 28. Missing data at this visit may be attributable to either premature discontinuation or subjects entering the extension study at Week 20 or Week 24. In both scenarios, missing data will be imputed using last observation carried forward (LOCF) where the last observed overall PASI score will be used to impute the missing data for all visits after the point of withdrawal or transition to the extension study. Missing data at other visits will also be imputed using LOCF (ie, if a subject has missing

at Week 12, for example, this will be imputed with the PASI score obtained at Week 8). In addition, PASI summaries will also be presented using observed cases.

There will be no imputation of missing individual item scores for the PASI; the LOCF imputation will apply to the overall PASI score only.

For the binary response variables (PASI25, PASI50, PASI75, PASI90 and PASI100), missing data will be imputed using nonresponder imputation (NRI), ie, subjects with missing data at a specific visit will be considered as nonresponders for the analysis. This will include visits after the point of withdrawal or after the point of transition to the extension study, if applicable. This will also be presented using observed cases.

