### 2.2.1 Clinical

Three clinical studies of bimekizumab have been completed: UP0008 in 39 subjects with mild to moderate plaque psoriasis, RA0124 in 30 healthy volunteers, and PA0007 in 53 subjects with psoriatic arthritis. Two studies (RA0123 and UP0031) are ongoing in subjects with moderate to severe rheumatoid arthritis and in healthy subjects, respectively.

UP0008 was a Phase 1, single ascending dose study in adults with mild to moderate psoriasis affecting  $\leq 5\%$  BSA. In this blinded study, single doses of up to 640mg (approximately 8mg/kg in an 80kg adult) were evaluated without any safety concerns. A total of 26 subjects with psoriasis with less than 5% of body surface involvement were treated with a range of single iv doses from 8 to 640mg. There were no clinically relevant safety findings identified at any dose and all doses were well tolerated. The pre-specified exploratory assessment of disease activity showed clinically relevant and statistically significant improvements at the higher doses studied.

RA0124 was a Phase 1, open-label, parallel-group, single-dose study in healthy subjects. The primary objective of this study was to determine the absolute bioavailability of single sc doses of bimekizumab (80mg and 160mg). The secondary objectives were to evaluate the dose proportionality of bimekizumab 80mg and 160mg sc, and to evaluate the safety and tolerability of these sc doses and 160mg given by iv infusion. In RA0124, the absolute bioavailability was

similar for the 2 doses tested (0.656 and 0.631 for the bimekizumab 80mg and 160mg sc doses, respectively). The PK of bimekizumab was linear in the tested dose range and the median  $t_{1/2}$  following sc administration was similar to that following iv administration (27.81 days and 28.25 days for bimekizumab 160mg sc and 160mg iv, respectively).

Bimekizumab has also been investigated in a Phase 1b, proof of concept, randomized, placebo-controlled, multiple dose study (PA0007). The primary objective of PA0007 was to assess the safety and PK of multiple dose administration of iv bimekizumab in subjects with psoriatic arthritis. Four active doses and a placebo were tested. Drug was administered as a loading dose at Week 0, and 2 additional doses were administered at Week 3 and Week 6. In each treatment group, subjects received a total of 3 doses of bimekizumab, administered every 3 weeks as shown below:

- 80mg loading dose followed by 40mg at Weeks 3 and 6

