### **3 STUDY OBJECTIVES**

#### **3.1 Primary objective**

The primary objective of this study is to evaluate the time-course of PASI over a 28-week period following the administration of bimekizumab given at Baseline and Week 4 to subjects with moderate to severe chronic plaque psoriasis.

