### **4 STUDY VARIABLES**

#### **4.1 Primary variables**

##### **4.1.1 Primary efficacy variable**

The primary endpoint of this study is change from Baseline in PASI at Week 28.

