##### Treatment Period

During the Treatment Period, subjects will be randomized 2:1 to receive the following blinded study treatment regimens:

- Treatment arm A: Bimekizumab 320mg administered sc at Baseline and Week 4, and placebo administered at Week 16
- Treatment arm B: Bimekizumab 320mg administered sc at Baseline and Weeks 4 and 16

There will be approximately 30 subjects in treatment arm A and 15 subjects in treatment arm B. Bimekizumab will be administered in the clinic at Baseline and Week 4, and at Baseline, Week 4, and Week 16 for those in treatment arm A and treatment arm B, respectively. Additional

nondosing study visits will occur at Week 2, Week 8, Week 12, Week 20, Week 24, and Week 28.

From Week 20 through Week 28, subjects who were previously PASI25 responders but subsequently relapse (defined as returning to a less than PASI25 response) will undergo the study assessments for that visit (ie, Week 20, Week 24, or Week 28) before receiving their first dose of study treatment in the extension study at Week 20, Week 24, or Week 28. Subjects eligible for the extension study must have the assessments for SFU conducted prior to entering the extension study. Subjects who have not achieved a PASI25 response at any visit prior to Week 20 will not be eligible to enter the extension study. All subjects not enrolling in the extension study will continue in PS0016 until the SFU Visit at Week 36.

Subjects withdrawing early from the study will undergo the Early Withdrawal Visit assessments (ie, Week 36) and will enter the SFU Period.

The assessments at each Treatment Period Visit are presented in [Table 5-1](#).

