8.1.2 Primary analysis of the primary efficacy variable

The individual scores for the PASI for each body region (redness, thickness and scaliness severity scores and area-of-involvement score [A]), and the derived total PASI score (from 0 to 72) will be listed for each subject and visit. The listing will include the change from Baseline and percentage change from Baseline for the total score only.

Descriptive statistics (including 95% CI) will be presented by treatment group and visit for absolute values, changes from Baseline and percentage change from Baseline (based on the total PASI score only). For the purpose of the tabulations the lower and upper 95% confidence limits will be truncated as follows:

- For the absolute values the lower 95% confidence limit will be truncated at 0 and the upper 95% confidence limit will be truncated at 72
- For the changes from Baseline the lower 95% confidence limit will be truncated at -72 and the upper 95% confidence limit will be truncated at +72
- For the percentage change from Baseline the upper 95% confidence limit will be truncated at +100%, there will be no truncation of the lower 95% confidence limit

The following figures will be presented:

- Combined individual (spaghetti) plots displaying percentage change from Baseline in PASI score versus time (visit) by treatment group (all subjects will be overlaid on the same plot with separate plots for each treatment group)
- Mean (with 95% CI) percentage change from Baseline in PASI score versus time (visit) by treatment group (both treatment groups will be overlaid on the same plot)

All tabulations and both individual and mean figures will be presented using the FAS and repeated for the PPS (if it differs from the FAS). All listings will be presented using the SS.

For subjects that discontinue the study or those that enter the extension study, missing data will be imputed using LOCF as described in Section 4.2.1.1 for the tabulations and mean figures.

Separate tables and mean figures will also be created based on the observed cases only. Missing data will not be imputed for the listings or the individual figures.

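### For Arm A, LOCF and observed cases will usually both overstate mean PASI response at Weeks 24 and 28, so the two planned estimates cannot bracket the primary quantity

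*SAP*

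**What the plan says.** Protocol 3.1 sets the primary objective: to "evaluate the time-course of PASI over a 28-week period following the administration of bimekizumab given at Baseline and Week 4". Protocol 4.1.1 adds: "The primary endpoint of this study is change from Baseline in PASI at Week 28". Protocol 5.1.1 defines the arm in question: "Treatment arm A: Bimekizumab 320mg administered sc at Baseline and Week 4, and placebo administered at Week 16".

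Protocol 5.1.1 and SAP 2.3 open early extension entry, at Weeks 20 to 28, to subjects who once reached PASI25 and have since dropped below it. Entry is allowed, not required. A subject who transitions has that visit's PASI assessed before the first extension dose.

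SAP 4.2.1.1 names two sources of missing Week 28 PASI: premature discontinuation, and transition at Week 20 or 24. For both, "missing data will be imputed using last observation carried forward (LOCF) where the last observed overall PASI score will be used", at every later visit. SAP 8.1.2 then says: "Separate tables and mean figures will also be created based on the observed cases only". Protocol 14.5 only says that imputation such as LOCF will be considered for PASI scores, and leaves any sensitivity analysis to the SAP. SAP 4.2 rules out imputations beyond those it lists, and no further sensitivity analysis of continuous PASI appears. The visit means carry 95% CIs; no test is planned.

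**The concern.** In Arm A the late part of the curve is where response is expected to be lost, and that loss is what the primary objective asks about. Missingness from transition is triggered by the outcome itself, since a subject must have relapsed to leave. Observed cases then average over those who remain, who are doing better. LOCF assumes no further change, so a subject who withdraws at Week 8 or 12 near peak response is shown near peak response at Week 28.

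If both planned estimates lean the same way, agreement between them is no reassurance. The 95% CIs do not show the problem either, because they treat carried values as measurements. The study is meant to guide Phase 3 dose selection (Protocol 1), so a flattered durability curve matters even in a descriptive analysis.

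**Working it through.** **No plan figure to reproduce.** The documents give no expected relapse rate, dropout rate, PASI SD or rate of response loss. N = 45 comes from a PKPD simulation whose model is not given, and this point does not depend on it. All sizes below are percentage points of PASI improvement and rest on stated assumptions.

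**Time off drug.** Protocol 2.2.1 gives half-lives of "27.81 days and 28.25 days for bimekizumab 160mg sc and 160mg iv, respectively". For Arm A, Week 4 to Week 28 is 24 × 7 = 168 days, and 168 / 27.81 = 6.0 half-lives. For Arm B, Week 16 to Week 28 is 84 / 27.81 = 3.0.

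**Bounds for relapsers.** Let q be the share who transition at Week 20 or 24.
- LOCF excess = q × (exit score − true Week 28 score). The exit score is below 25, so without rebound above Baseline the excess is below 25q: q = 10% (3 of 30), under 2.5; q = 20% (6 of 30), under 5.0; q = 30%, under 7.5.
- Observed-case excess = q × (stayer mean − relapser mean). With stayers at 70% and relapsers at 0 to 10%: q = 10%, 6 to 7; q = 20%, 12 to 14; q = 30%, 18 to 21.

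Per relapser, observed cases is the larger error.

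**Withdrawal while responding.** With an assumed peak of 93% and a true Week 28 mean of 46.3%, each such subject in 30 adds (93 − 46.3) / 30 = 1.6 points to the LOCF mean.

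**Counterexample.** A subject lost at Week 2 (about 45.3% improved) whose true Week 28 value is 70% adds (45.3 − 70) / 30 = −0.8.

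**Simulation.** Arm A, 20,000 subjects per scenario: mean peak 93%; logistic loss of response with mean midpoint at Week 32, 28 or 24; every subject below PASI25 at Week 20 or 24 transitions; random dropout 0, 10 or 20%; rebound 0 or 10% above Baseline. The last column is a multivariate-normal likelihood fit, of the mixed-model type, on a subset of 6,000. Selected Week 28 results:

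| Midpoint, dropout, rebound | Transition % | Truth | LOCF error (relapsers + withdrawals) | Observed-case error | Likelihood error |
|---|---|---|---|---|---|
| 32, 0%, 0 | 3.2 | 64.0 | +0.4 (0.4 + 0) | +2.0 | −1.2 |
| 28, 0%, 0 | 12.0 | 46.3 | +1.4 (1.4 + 0) | +5.7 | −3.5 |
| 28, 10%, 0 | 11.0 | 46.5 | +4.6 (1.3 + 3.4) | +5.8 | −3.5 |
| 24, 10%, 0 | 25.1 | 26.7 | +7.4 (2.9 + 4.5) | +8.5 | −4.7 |
| 24, 20%, 0 | 23.1 | 27.0 | +11.6 (2.7 + 8.9) | +8.5 | −5.2 |
| 24, 20%, 10% | 29.5 | 19.3 | +15.1 (4.9 + 10.2) | +12.8 | −10.3 |

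(Components may not add exactly because of rounding.) In all 18 scenarios LOCF and observed cases were high and the likelihood fit was low. A separate set of 32 Arm A scenarios gave LOCF +0.1 to +11.2, observed cases +0.4 to +16.4 and likelihood −0.2 to −19.3. A third set of 30, with other loss speeds, reached about +17 for both planned estimates.

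**In PASI units.** At an assumed Baseline PASI of 20, +11 points is 0.11 × 20 = 2.2 and +16 points is 3.2. At the entry minimum of 12 they are 1.3 and 1.9.

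**The case against.** The strongest case for the plan has five parts.

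- **Relapsers under LOCF stay in as near-failures.** Their carried score is already below 25% improvement, so the excess from them is small. This stands. Most of the larger LOCF errors come from assumed withdrawals during response.
- **Not every relapser leaves.** Extension entry is optional, so observed cases keep those who stay. The Week 20 mean is untouched by transition, because leavers are assessed first. This also stands; the effect of transition is confined to Weeks 24 and 28.
- **Withdrawers give more data.** They have an Early Withdrawal PASI and a Safety Follow-Up PASI 20 weeks after the last dose, about Week 24 if that dose was at Week 4. SAP 4.4 maps the first to a scheduled visit but has no rule that places the second at Week 24, so it does not repair the mean as written.
- **Other outputs show the relapse.** NRI response curves count leavers as failures; in the simulation, Week 28 PASI75 under NRI was at or below the truth. Individual plots are unimputed, disposition counts relapses and transitions, and a pooled PKPD model is planned. These mitigate the problem, but none corrects the Week 28 mean and its CI.
- **The analysis is exploratory and descriptive.** True, but this mean curve is still the primary result.

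A reader might go further and infer that both estimates must overstate response. The documents do not support that. LOCF understates for a subject lost before peak response, and could do so in Arm B if someone below PASI25 at Week 20 would still have improved after the Week 16 active dose. A reader might also infer that a mixed model gives the right answer and should replace LOCF. It does not: when every relapser leaves, nobody below PASI25 is observed later and the model must extrapolate, and it erred downward in every scenario, often by more than LOCF erred upward.

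**Conclusion.** The point holds in a limited form. For Arm A, both planned estimates of the continuous PASI course will usually overstate mean response at Weeks 24 and 28. The observed-case limb follows from the transition rule whenever relapsers use it. The LOCF limb depends mainly on how many subjects withdraw while responding.

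The plausible Week 28 excess is about 0 to +11 points for LOCF and 0 to +16 for observed cases, somewhat more under faster loss, higher dropout or rebound. With few transitions and no dropout it is negligible for LOCF. Week 24 shares the mechanism but was not sized. Overstatement is judged against the PASI course without retreatment, which Protocol 3.1 implies but neither document states.

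This is a cheap improvement. It does not make the descriptive results unusable, and it does not touch the NRI response curves.

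**What to change.** In SAP 4.2.1.1 and 8.1.2:

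1. State that the target is the PASI course to Week 28 without retreatment in the extension study.
2. Keep LOCF and observed cases as planned.
3. Add two pre-specified estimates of the visit means with 95% CIs:
   - (a) a mixed model for repeated measures on all observed PASI changes to Week 28, with visit, arm-by-visit after Week 16 and Baseline PASI, and a named fallback covariance;
   - (b) the same analysis with transitioners' post-exit visits set to their Baseline PASI.
4. Present the estimates together as a bracket, and do not describe the mixed model as unbiased.

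Estimate (b) limits the extrapolation. If relapsers' true Week 28 improvement is 0 to 10%, it understates their part by q × (0 to 10), so at most 2 points at q = 20%. With 10% rebound it overstates that part by at most the same amount.

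The cost is SAP wording and two extra outputs. Eight post-Baseline visits to Week 28 give 8 × 9 / 2 = 36 unstructured covariance parameters for 45 subjects, so the fallback may well be needed and should be named in advance.

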#### Safety Follow-Up Period

All subjects not continuing in the extension study, including those withdrawn from study treatment, will have a SFU Visit 20 weeks after their last dose of study medication (ie, bimekizumab or placebo).

The assessments for the SFU Visit are presented in [Table 5-1](#).

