**Table 7–1: Prohibited psoriasis medications**

Drug	Exclusion criteria prior to Baseline Visit
Any other antipsoriatic agent (systemic) under investigation (or approved after the protocol is approved)	24 weeks
Topical corticosteroids for dermatological use Vitamin D analogues and topical retinoids Keratolytic and coal tar	2 weeks
Any other antipsoriatic agent (topical) under investigation	4 weeks

IL-17=interleukin 17; TNF=tumor necrosis factor

Subjects who take prohibited medications, except topical therapies, may be withdrawn from study treatment but followed until the Safety Follow-Up. The decision to withdraw a subject for taking prohibited medications should be made in consultation with the Medical Monitor. As noted above, subjects that use prohibited topical medications will be allowed to stay in the study but will be counseled to not use them further.

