#### **14.5 Handling of dropouts or missing data**

For the primary efficacy analysis, missing data will be imputed using NRI. That is, subjects with missing data at Week 28 or who discontinue study treatment prior to Week 28 will be counted as non-responders for the analysis. Imputations (such as LOCF) will be considered for missing PASI scores for summary statistics and changes from baseline. More details will be included in the SAP. Sensitivity analyses may be performed and will be detailed in the SAP.

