4.2.1.3 Investigator's Global Assessment

There will be no imputation of missing individual data for the IGA score. For the responder analysis, missing data will be imputed using NRI, ie, subjects with missing data at a specific visit will be considered as nonresponders for the analysis. This will include visits after the point of withdrawal or after the point of transition to the extension study, if applicable. In addition, IGA summaries will also be presented using observed cases.

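### The SAP ties non-response to missing data alone and has no scoring rule after treatment discontinuation or prohibited psoriasis therapy, so such subjects can count as responders

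*SAP*

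**What the plan says.** **Protocol.** Section 14.5 gives two triggers for non-response: "subjects with missing data at Week 28 or who discontinue study treatment prior to Week 28 will be counted as non-responders for the analysis". It adds that LOCF will be considered for PASI scores and leaves details to the SAP.

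Section 7.8.2 covers prohibited psoriasis therapy. For systemic therapy and phototherapy: "Subjects who take prohibited medications, except topical therapies, may be withdrawn from study treatment but followed until the Safety Follow-Up". For topicals: "subjects that use prohibited topical medications will be allowed to stay in the study but will be counseled to not use them further". Section 5.1.1 adds: "All subjects not continuing in the extension study, including those withdrawn from study treatment, will have a SFU Visit 20 weeks after their last dose". PASI and IGA are recorded at that visit (section 8.11).

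**SAP.** Section 4.2.1.1 keeps one trigger for the PASI response variables: "subjects with missing data at a specific visit will be considered as nonresponders for the analysis". It continues: "This will include visits after the point of withdrawal or after the point of transition to the extension study, if applicable". Section 4.2.1.3 follows suit for IGA: "For the responder analysis, missing data will be imputed using NRI". Section 4.2 closes the list: "No other imputations will be performed".

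Section 4.4 assigns Early Withdrawal Visit values to a scheduled visit. Section 3.9 lists three departures from the protocol analyses (FAS definition, individual plots, adverse event cut-off); the NRI rule is not among them. Response tables use the FAS (8.2, 8.3). The PPS repeat is specified only for the PASI score and change outputs (8.1.2).

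**The concern.** There are two gaps. First, the protocol's treatment-discontinuation trigger has dropped out of the SAP without being declared. Section 1 of the SAP says the protocol governs unless the SAP specifies otherwise, so two programmers could produce different response tables and each defend the result.

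Second, neither document says how a PASI or IGA value is scored once the subject has started another psoriasis therapy. Such a value is not missing, so NRI never reaches it.

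The study asks how PASI behaves over 28 weeks, including the time after active dosing stops. A response held up by another therapy would be read as persistence of the bimekizumab effect, and this study is meant to guide Phase 3 dose selection.

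**Working it through.** **1. Plan figures.** No stated figure depends on this rule. The total of 45 comes from PKPD simulation pooled with PS0010, and the model is not given, so it cannot be recomputed. The 2:1 split can: 45 × 2/3 = 30 in arm A and 45 × 1/3 = 15 in arm B, as stated.

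**2. The rules side by side.**

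| Situation at a visit | Protocol 14.5 (Week 28) | SAP 4.2.1.1 and 4.2.1.3 |
|---|---|---|
| Value missing | Non-responder | Non-responder |
| Study treatment discontinued, value observed | Non-responder | Depends on what withdrawal means |
| Prohibited therapy, value observed | No rule | No rule; value used as observed |

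If withdrawal in the SAP means leaving study drug and every later visit is imputed, the second row agrees with the protocol. If it means leaving the study, or if only missing later visits are imputed, the second row is scored at face value. The text does not settle which.

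**3. Can observed values arise?** Yes, by three routes:

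- Prohibited therapy. Topical users stay in the study. Withdrawal of other users from study treatment is optional, and they are followed.
- An Early Withdrawal Visit, whose PASI and IGA are mapped to a scheduled visit as observed data.
- The Safety Follow-Up Visit, 20 weeks after the last dose: Week 0 + 20 = 20, Week 4 + 20 = 24, Week 16 + 20 = 36.

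**4. Which visits?** Week 16 is assessed before the third dose (protocol 8.7). For the Week 16 secondary endpoints, exposure differs from plan only if the Baseline or Week 4 dose was missed, so the gap lies mainly at Weeks 20 to 36. No dose follows Week 16. For a subject who has had all three, the discontinuation clause in protocol 14.5 would not capture therapy started later, so restoring that clause alone does not close the second gap.

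**5. Does a planned response table remove the effect?** No. The observed-case tables keep the same observed responders and change only the denominator (SAP 8.3.1, 8.3.2). There is no PPS version of the response tables.

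**6. Size.** One responder rescored as a non-responder lowers the rate by 1/n: 1/30 = 3.3 points in arm A and 1/15 = 6.7 points in arm B. The number of such subjects, k, is not in the documents. For illustration, take k = 1 to 3 and an observed rate of 80% (both assumptions), with the SAP's Wilson 95% interval:

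| k | Arm A | Arm B |
|---|---|---|
| 0 | 24/30 = 80.0% (62.7 to 90.5) | 12/15 = 80.0% (54.8 to 93.0) |
| 1 | 23/30 = 76.7% (59.1 to 88.2) | 11/15 = 73.3% (48.0 to 89.1) |
| 2 | 22/30 = 73.3% (55.6 to 85.8) | 10/15 = 66.7% (41.7 to 84.8) |
| 3 | 21/30 = 70.0% (52.1 to 83.3) | 9/15 = 60.0% (35.7 to 80.2) |

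The face-value B minus A difference exceeds the rescored one by k_B/15 − k_A/30. One subject in arm A alone narrows the difference by 3.3 points; one in arm B alone widens it by 6.7. The direction is therefore not fixed.

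**The case against.** The case for leaving the plan alone has real weight.

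- **The protocol sentence fits poorly.** It is written for the primary analysis at Week 28, yet the primary variable is continuous PASI change, for which responder status has no meaning. It also defers to the SAP. This stands, and it makes the first gap one to reconcile or declare. A reader might infer that the SAP dropped a protocol rule on prohibited therapy; protocol 14.5 contains none.
- **The drug-stop route is narrow.** Beyond the Early Withdrawal Visit and the follow-up visit, the protocol does not clearly require visits after treatment stops, and unattended visits are scored as non-response. Stopping drug also does not imply starting another therapy. This stands.
- **Relapse has an exit.** Previous PASI25 responders who fall below PASI25 at Weeks 20 to 28 can enter the extension, and NRI then applies. But a subject who has lost PASI75 while keeping PASI25 does not meet that relapse definition. That such subjects might turn to other therapy is inference, not something the documents report.
- **Review before unblinding.** Prohibited medication is a category of important deviation, and the data evaluation meeting may decide how to handle problem data (SAP 3.4). That is discretion, not a stated rule, and without PPS response tables an exclusion from the PPS would not show in them.
- **Exploratory purpose.** No between-arm efficacy test is planned, and response at Weeks 20 to 36 is an other variable. This limits the consequence but does not supply the missing rule.

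**Conclusion.** The point holds as a gap in specification. The SAP is narrower than protocol 14.5, or at best ambiguous, and does not say so; prohibited therapy has no scoring rule in either document. A subject in these situations *can* be counted as a responder, provided the observed value meets the threshold, at 3.3 points per subject in arm A or 6.7 in arm B. Any total rests on an assumed number of subjects.

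Three stronger readings are not supported. The SAP does not automatically score such subjects as responders. The effect is not shown to favour one arm: heavier use of other therapy in arm A is plausible but undocumented. Nor does NRI scoring affect the primary endpoint, which is continuous, uses LOCF and has a planned PPS repeat, although that endpoint too lacks a rule for values on prohibited therapy.

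**What to change.** 1. In SAP 4.2.1.1 and 4.2.1.3, define withdrawal (from study drug or from the study). Align NRI with protocol 14.5, or list the departure in SAP 3.9. State that missing only the Week 16 placebo injection in arm A does not by itself make a subject a non-responder, since that subject has had the full active regimen of the primary objective.
2. Score visits after the start of a Table 7-1 systemic therapy or phototherapy as non-response. Handle topical use in a sensitivity table; permanent non-response after a single topical use would be too severe.
3. Repeat the PASI and IGA response tables on the PPS. Keep the planned observed-case tables as the face-value analysis.
4. For continuous PASI and BSA, do not replace on-therapy values by LOCF in the main table, because the carried value may predate relapse and overstate durability. Flag the affected values, and rely on the planned PPS repeat for PASI.

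The cost is SAP wording, a flag built from medication and discontinuation data already collected, and a few more tables. Response rates may be slightly lower.
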